
8. Project Narrative

Treatment of schizophrenia currently includes antipsychotic medications and cognitive therapies which improve some symptoms, but do not sufficiently restore cognitive functioning or reduce psychosocial disability. We hypothesize that medications that specifically target sensory information processing deficits, rather than psychotic symptoms per se, will significantly enhance the benefits of a sensory-based targeted cognitive training (TCT) intervention in patients with schizophrenia. We will complete a randomized, double-blind clinical trial to: 1) confirm that the drug memantine augments TCT learning; 2) determine whether memantine enhances the clinical benefits from a full 30 session course of TCT vs. TCT plus placebo in antipsychotic-medicated schizophrenia patients, and 3) determine if memantine's enhancement of TCT is most effective in biomarker-defined subgroups of patients.

SPECIFIC AIMS: Memantine Augmentation of Targeted Cognitive Training in Schizophrenia

Cognitive impairment affects the majority of patients with schizophrenia (**SZ**) and directly contributes to their psychosocial disability. Unfortunately, treatment approaches designed to improve cognition in SZ have been limited. Recent findings demonstrate that cognitive functioning in SZ can be improved by interventions that leverage neuroplasticity-based perceptual learning mechanisms. “Targeted Cognitive Training” (**TCT**) is a computerized intervention designed to sharpen the acuity and fidelity of sensory information processing through specific exercises that systematically increase demands on early perceptual and attentive processes. For many participants, TCT leads to “bottom-up” gains in perceptual functioning that lead to improvements in verbal learning and memory after 20-30h. While these benefits of TCT are evident at the group level, nearly half of all patients fail to show cognitive gains, even after extended 40-100h courses of TCT. For patients, their families, clinicians and health systems, the costs and logistical complexities associated with these time- and resource-intensive interventions, even under optimized conditions, can be prohibitive.

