A novel approach to bridge this divide between the therapeutic promise of TCT and its mixed effectiveness is to combine TCT with an intervention that augments the clinical gains of TCT. This application responds to RFA-MH-18-705 by conducting efficient pilot testing of a novel intervention strategy for chronic psychotic disorders - **Pharmacologic Augmentation of Cognitive Therapy (PACT)** - via an experimental medicine approach. We propose to test a novel “augmentation strategy” of daily dosing of 20 mg of memantine to enhance the benefits of TCT in stable, antipsychotic medicated SZ patients.

Memantine is a non-competitive NMDA receptor modulator which is currently FDA-approved for the treatment of moderate-to-severe Alzheimer’s disease, and is often used adjunctively in a variety of neuropsychiatric illnesses, including SZ. Recent meta-analyses of memantine augmentation in antipsychotic-medicated SZ patients have demonstrated its safety, tolerability and modest effectiveness at improving cognition. **We hypothesize that memantine will augment TCT learning (Aim 1) and hence the clinical gains from TCT (Aim 2), and that this PACT approach will be particularly effective in biomarker-defined subgroups of patients (Aim 3).**

Preliminary support for these hypotheses and the proposed design comes from both laboratory- and clinic-based studies conducted over the past decade. **In our laboratory**, we have tested both dose-effects of a single pill of memantine on neurophysiological measures of early auditory information processing (EAIP) and TCT learning in antipsychotic-medicated SZ patients. In these studies, memantine (20 mg > 10 mg = 0 mg) significantly enhanced several EEG-based measures of EAIP, as well as learning in an auditory discrimination task -- a key component of the TCT suite of exercises with established efficacy in SZ patients. Although memantine-enhanced TCT learning during a 1h Sound Sweeps test provides a valuable assay of “target engagement”, we do not yet have evidence that it predicts greater, faster or more lasting clinical, neurocognitive or functional gains with a full course of memantine+TCT.

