General Methods: Environment: Subjects are screened, tested and undergo TCT at the UCSD Medical Center. Participants are 18-55 y.o. AP-medicated (stable regimen \geq 1 month, in active outpatient treatment) patients with a primary diagnosis of SZ or schizoaffective disorder (depressed type), recruited and consented at UCSD as per^{49,59,74}. Study inclusion/exclusion criteria are detailed in "**Protection of Human Subjects**". Screening includes a confirmatory diagnostic assessment (M.I.N.I. 6.0), a general medical, psychiatric and substance history, physical exam by an M.D., EKG, vision and hearing tests, urine toxicology and pregnancy test (UTox/P). All medications and changes are recorded (AP doses in chlorpromazine equivalents; quantifying anticholinergic burden⁹⁵ as in^{33,48,49}). Medication patterns of our last \approx 100 SZ subjects are published elsewhere^{49,74,96}.

Design (Fig. 5). Enrolled patients complete clinical, neurocognitive and functional measures and candidate biomarkers (EEG, QuickSIN, WIN) tested in Sound Sweeps at baseline, and then assigned to PBO vs. MEM arms (n=27/arm) using stratified random sampling (over sex, age and high/low Test 1 (baseline) APS learning) blind to arm identity. Stratifying for baseline APS learning should increase the sensitivity of the primary target engagement metric. Test 2 follows \approx 5-7 days later, after either PBO or MEM (20 mg po). Tests 1-2 are used to assess target engagement (Aim 1: MEM-enhanced APS learning) as well as MEM effects on ERP/EEG, auditory discrimination (QuickSIN, WIN) and neurocognitive measures (Aim 3: Biomarkers). Our design allows for 20% attrition from enrollment (n=69) to completion of target engagement testing (n=54).

For Aim 2, all participants will be titrated up to 20 mg MEM or Placebo over a 3-week period and concurrently begin TCT 3 d/week (M-W-F) for 1-h/d (recognizing the need for flexibility, T-Th are "make-up days"), and continues until a subject completes 30-h (\approx 10-12 weeks). TCT is delivered by trained staff (see below). Patients and staff are blind to study arm; staff are blind to patients' baseline, interval, and post-intervention assessments.

[figure not shown]

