Aim 1 – Confirm target engagement: The primary dependent measure of target engagement is MEM-enhanced APS learning. APS learning is defined as the reduction in Sound Sweeps APS threshold (ms) Test 1 to Test 2 assessment. Target engagement was demonstrated in Fig. 3⁷⁶, and will be confirmed if APS learning is increased by MEM (note that MEM and PBO groups are matched by Test 1 PBO performance via stratified randomized assignment). As appropriate, effect sizes and inferential statistics are based on standard regression or LME models with random intercepts. A significant interaction between contrast coded drug (PBO vs. MEM) and Test (Test 1 vs. Test 2) predictors on APS learning is a “Go” criteria and confirms target engagement.

Aim 2 – Test clinical, neurocognitive and functional impact of MEM on TCT, and its relationship to target engagement: We will determine if MEM+TCT produces greater, faster or more durable clinical, neurocognitive or functional gains from baseline, compared to PBO+TCT, over a 30-session course of TCT. A Cohen’s $d > 0.5$ for the main effect of drug (PBO vs. MEM) or drug x session (#10, 20, 30) interaction in an LME model is the primary “Go” criteria. The effect of drug assesses “greater” gains. Reverse Helmert contrasts for session assesses “faster” gains. A separate model comparing differences in outcomes at 12-weeks post-TCT assesses “more durable” gains. Secondary analyses will examine whether change in MEM-enhanced APS learning (“within-subject” target engagement; Aim 1) predicts gains in Aim 2 outcome measures.

Aim 3 – Biomarkers of MEM-induced gains: We will determine if baseline levels of specific neurocognitive or EEG-based measures, or changes in specific measures with initial MEM exposure (Test 2 vs. 1), predict greater sensitivity to MEM-enhanced neurocognitive, clinical or functional gains over 30-h of TCT. Regression analyses will assess whether specific candidate biomarkers predict MEM-enhanced gains in outcome measures.

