"Go/No-Go" decisions are based on traditional statistical significance (Aim 1) and effect sizes (Aim 2). Formal statistical testing is conducted using linear mixed-effects (LME) models; hypothesis tests are 2-sided ($\alpha=0.05$). Model parameters are estimated via the R lme4 package and Cohen's d is estimated via the EMAtools package. Type I errors are minimized by constraining the number of primary analyses; secondary analyses use false discovery rate corrections.

PANSSt scores will be assessed at specific intervals. Because TCT is associated with improvements in both positive and negative symptoms, our *a priori* hypothesis is that a PACT effect will be evident in both positive and negative symptoms. Hence, PANSSt is used as the primary metric of symptomatic gains. A greater reduction in PANSSt score will be detected using data from baseline through TCT 30h, by a significant main effect of group (arm) or a significant interaction of group x session, with post-hoc contrasts revealing significant group differences at TCT 30h. A faster reduction in PANSSt scores will be detected using these same data by a significant interaction of group x session and a significant group difference at a point prior to TCT 30h. A more durable reduction in PANSSt scores will be detected using data from TCT 30h through 12 weeks post-TCT, by a significant main effect of arm or a significant interaction of group x post-TCT day, with post-hoc contrasts revealing significant group differences 12 weeks post-TCT.

Comparable analytic approaches will be used for neurocognition (MCCBc) and function (WHODAS) as described in "Research Strategy". Data will be described as means with SEM. Tests for normalcy will be applied to all data and non-parametric comparisons will be used if normalcy is not demonstrated. The Analysis Set for these data will be all subjects who have completed 30h of TCT and post-TCT clinical, neurocognitive and function assessments. When appropriate, missing data are handled via multiple imputation or full information maximum likelihood estimation.

Secondary regression analyses assess the predictive value of putative biomarkers on clinical, neurocognitive or functional gains from the addition of MEM to TCT. Future studies with larger samples will assess potentially more informative models, e.g. Path Analysis to study moderating effects of APS MEM sensitivity and biomarkers on both indirect (moderated-mediation) and direct paths between treatment and outcome.

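### The plan gives no single estimand for 'greater' gains, and its visit-averaged drug effect understates an end-of-treatment benefit that builds up with training

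*Combined protocol and SAP*

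**What the plan says.** Three places define greater gains, and they differ.

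- **Research Strategy, Data Analysis, Aim 2.** The primary Go criterion is d above 0.5 "for the main effect of drug (PBO vs. MEM) or drug x session (#10, 20, 30) interaction in an LME model". The text then assigns the terms: "The effect of drug assesses “greater” gains". Reverse Helmert contrasts for session carry faster gains, and a separate 12-week model carries more durable gains.
- **Section 4.4, Go/No-Go decision and primary and secondary endpoints.** "A greater reduction in PANSSt score will be detected using data from baseline through TCT 30h", by a significant group main effect or a significant group-by-session interaction, "with post-hoc contrasts revealing significant group differences at TCT 30h". MCCB composite and WHODAS are to be handled comparably.
- **Table 1.** Row 2 asks for MEM+TCT to exceed PBO+TCT on any of the three measures and names no visit. Row 3 gives the drug-by-session interaction to faster gains, requires p<0.05, and follows it with a group difference at some session or combination of sessions.

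The Outcome and Go Decisions text justifies the 0.5 threshold as a visible, clinically meaningful change. Both analysis sections say that d comes from the EMAtools package; neither states which SD is the denominator.

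**The concern.** The threshold is argued for as the gain that a course of PACT should deliver, but in the Aim 2 text it is applied to an average over the course. The plan's mechanism is learning that accumulates over sessions, and it calls TCT efficacy dose-dependent. If the drug benefit grows in the same way, a visit average sits below the session-30 difference, so demanding 0.5 of the average demands more than 0.5 at the end of treatment.

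Section 4.4 pulls in two directions. It takes the main effect from data that include baseline, where randomised arms should not differ, yet it names the 30-hour difference as the contrast to be shown. It also asks for significance, which the Outcome and Go Decisions text declines to require for Aim 2. The same data could therefore pass or fail on greater gains depending on which definition the analyst follows, in a rule that decides whether a confirmatory trial goes ahead.

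**Working it through.** **The plan's own figures.** The documents give no power or expected d for an averaged Aim 2 effect. The NNT quoted for d = 0.5 does reproduce: 1/(2Φ(0.5/√2) − 1) = 3.62. The 27 per group is an Aim 1 figure and is not affected here.

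**What the drug main effect estimates.** Reverse Helmert contrasts sum to zero over the session levels. With a drug-by-session term in the model, the drug coefficient is then the equal-weight mean of the arm differences at sessions 10, 20 and 30.

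**Effect of averaging.** Take a true session-30 d of 0.5 on a single-visit SD. The accrual shapes are assumptions.

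| Accrual (fraction at 10, 20, 30) | Mean of three visits | Mean with baseline (0) as a fourth |
|---|---|---|
| Immediate, flat (1, 1, 1) | 0.50 | 0.375 |
| Plateau by session 20 (1/2, 1, 1) | 0.42 | 0.31 |
| Linear (1/3, 2/3, 1) | (0.167+0.333+0.500)/3 = 0.33 | 1.000/4 = 0.25 |
| Session 30 only (0, 0, 1) | 0.17 | 0.125 |

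**Chance that the estimate reaches 0.5.** Inputs: 18 completers per arm (Subject throughput); correlation ρ = 0.8, borrowed from the Aim 1 power statement and assumed equal between all visits; baseline adjustment; raw between-patient SD of 1; linear accrual.

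- Session-30 contrast: residual variance 1 − 0.8² = 0.36; SE = √(2×0.36/18) = 0.200; P = 50%.
- Three-visit mean: variance (1 + 2×0.8)/3 = 0.867; residual 0.867 − 0.64 = 0.227; SE = √(2×0.227/18) = 0.159; z = (0.5 − 0.333)/0.159 = 1.05; P = 15%.
- For a true session-30 d of 0.7, the mean is 0.467. The chances are 84% (z = −0.2/0.200) and 42% (z = 0.033/0.159).

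**Sensitivity to the SD and correlation** (true session-30 raw-SD d of 0.5, linear accrual, same method).

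- ρ = 0.8, average scaled by the SD of the patient's three-visit mean, √0.867 = 0.931: it reads 0.333/0.931 = 0.36, P = 20%, against 50% for session 30.
- ρ = 0.8, both scaled by the SD of change: √(0.867 + 1 − 1.6) = 0.516 for the average and √0.4 = 0.632 for session 30. They read 0.65 and 0.79, with P = 68% and 82%.
- ρ = 0.5, raw SD: SE of the mean = √(2×(0.667 − 0.25)/18) = 0.215; z = 0.167/0.215 = 0.77; P = 22%, against 50%.

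The average is the harder test in every case, but by 35 points in the base case and 14 points on the change-score SD.

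**The interaction route.** Under linear accrual, session 30 minus the mean of sessions 10 and 20 is 0.5 − 0.25 = 0.25. Its SD is √(1.5(1 − ρ)), so d = 0.46 at ρ = 0.8 and 0.29 at ρ = 0.5. At 18 per arm, z = d×√9 = 1.37 or 0.87, so the p<0.05 step in Table 1 row 3 has power of about 28% or 14% on this contrast.

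**The case against.** **The Go rule is an OR.** This is the strongest reply. The Aim 2 sentence accepts the interaction as an alternative, Table 1 needs only one of rows 2 to 4, and week 12 is a separate route. Simulations of ramping effects (ρ 0.5 and 0.8, 18 and 27 per arm, each term scaled by its own SD) put the chance that the main effect or the session-30 Helmert contrast exceeds 0.5 at 51–78%, against 22–40% for the main effect alone. A reader might infer that a treatment truly at the threshold would mostly be called No-Go. The documents do not support that for the rule as a whole. The reply is incomplete, however, because those percentages leave out row 3's p<0.05 step, and Section 4.4 also requires a significant group difference before 30 hours for faster gains.

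**An average is a legitimate estimand.** For a pilot with about 18 completers per arm it is more precise, and with an immediate, flat effect nothing is lost. That stands. But the plan does not choose it consistently, since Section 4.4 already points to the 30-hour difference.

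**Session 10 as an empty visit.** A reader might also infer that session 10 cannot carry a drug effect. At 65 days per 30 sessions it falls near day 22, and the Design text says "all participants will be titrated up to 20 mg MEM or Placebo over a 3-week period and concurrently begin TCT 3 d/week". The Specific Aims equate 10 mg with 0 mg and speak of "gains in perceptual functioning that lead to improvements in verbal learning and memory after 20-30h". Counting only full-dose sessions (1, 11 and 21 of 21) would give 0.02, 0.26 and 0.50, mean 0.26. The documents do not carry this reading:

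- The 10 mg result comes from single-pill studies, and the plan itself says that one dose and repeated doses act differently.
- The titration has a 15 mg/day step on which no result is reported.
- The 20–30 h timing concerns verbal learning and memory, not PANSS total or WHODAS.
- The plan also hypothesises faster gains.
- Sections 4.2.a and 4.4 describe 20 mg taken 60 minutes before each session, with no titration.

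**Conclusion.** The point holds as an undefined and internally conflicting estimand on the greater-gains route. The Aim 2 text, Section 4.4 and Table 1 do not ask for the same quantity. The version that carries the d threshold understates any benefit that builds up over the 30 sessions. Under linear accrual, 0.5 at session 30 reads as 0.33, or 0.25 if baseline is a modelled visit; the three-visit range is about 0.17 to 0.50. The contrast of about 15% with 50% rests on linear accrual, 18 per arm, correlation 0.8, baseline adjustment and raw SD. The documents fix neither the accrual shape nor the SD for d, and other SDs narrow the gap. The interaction and week-12 routes can still give a Go.

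Separately, the titrated daily regimen (Design; Specific Procedures) and 20 mg before each session (Sections 4.2.a, 4.2.c and 4.4) contradict each other and must be reconciled. The linear-accrual figures do not depend on which applies.

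**What to change.** In Table 1 row 2, the Aim 2 analysis text and Section 4.4, use one definition for PANSS total, MCCB composite and WHODAS: the model-estimated MEM minus PBO difference in change from baseline at session 30. Take it from the same mixed model with all visits kept, and do not count baseline in the drug effect. Apply d ≥ 0.5 to that contrast, state the SD used for d, and use sessions 10 and 20 for faster gains. Settle this before unblinding.

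The cost is wording only, with no new visits or patients and no change to dosing. The session-30 contrast is somewhat less precise than a visit average (SE 0.200 against 0.159 in the base case). A benefit that appears early and fades would be credited under faster gains.

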Outcome and “Go Decisions”. In addition to confirming “target engagement”, this application tests the hypothesis that SZ patients given MEM +TCT will exhibit greater, faster and/or more durable improvements (change from baseline) in symptoms, neurocognition and/or function compared to patients given PBO+TCT, and that this enhanced clinical response will be associated with greater MEM-enhanced TCT learning.

The small “n” necessitated by the 3-year timeline and demanding treatment schedule greatly constrains the total number of outcome measures.

Moreover, the plan to assess not only magnitude but also rate and durability of PACT gains triples the number of primary analyses. Thus, we selected only one **primary** clinical, neurocognitive and functional outcome measure (Table 1) – recognizing that they are relatively “blunt” metrics - but will track several other, more focused, measures as well as inter-measure correlations in exploratory analyses to inform future studies.

A “Go” decision requires: 1) confirmation of target engagement (APS learning, MEM>PBO, p<0.05); 2) evidence of gains from PACT ($d \geq 0.5$ (MEM > PBO)) in primary clinical, neurocognitive and/or functional measures (Table 1), and 3) the absence of adverse effects of MEM that are significantly greater than PBO levels. The decision to not use traditional statistical significance as “Go” criteria for Aim 2 reflects this RFA’s call for “Pilot” studies, the need to identify candidate treatments for a subsequent larger “n” Confirmatory Efficacy R01 study, and the limits in sample size resulting from the 3-year R33 duration. Cohen defined a medium effect size ($d=0.5$) as one that is “visible to the naked eye,” and this amount of change is viewed as clinically meaningful in trials targeting negative symptoms.⁹⁹⁻¹⁰¹ This $d=0.5$ “Go” threshold for Aim 2 corresponds to a “number needed to treat” (NNT) value ≈ 3.62 . While a “Go” decision does not require identification of a biomarker predicting greater PACT sensitivity (Aim 3), the identification of one or more meaningful predictors that could be incorporated into a Confirmatory Efficacy trial would favorably impact a “Go” decision.

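### The Aim 2 Go cut of d > 0.5 is applied to the drug-by-session interaction itself, where it neither measures the drug's benefit nor identifies faster gains, and conflicts with Table 1 and section 4.4

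*Combined protocol and SAP*

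**What the plan says.** Research Strategy, Data Analysis, Aim 2 paragraph: the Go cut is a Cohen's d above 0.5, which "for the main effect of drug (PBO vs. MEM) or drug x session (#10, 20, 30) interaction in an LME model is the primary" criterion. The drug effect is assigned to greater gains. For faster gains the text says "Reverse Helmert contrasts for session assesses" them. Durability has a separate model at 12 weeks after training.

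Outcome and Go Decisions: a Go requires "evidence of gains from PACT ($d \geq 0.5$ (MEM > PBO)) in primary clinical, neurocognitive and/or functional measures (Table 1"). The number is defended as a medium, clinically meaningful effect, and the "threshold for Aim 2 corresponds to a “number needed to treat” (NNT) value ≈ 3.62".

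Table 1, under a d > 0.5 heading, states item 3 (faster) differently. The interaction must reach p < 0.05, and MEM+TCT must then exceed PBO+TCT at a session or combination of sessions.

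Section 4.4, Go/No-Go decision and endpoints: on data from baseline to 30 h of training, a faster PANSS reduction needs a significant interaction plus a significant group difference at a point before 30 h. MCCB and WHODAS are handled comparably. On the effect size, the section says only "Model parameters are estimated via the R lme4 package and Cohen's d is estimated via the EMAtools package". No section gives the formula for d or the SD behind it.

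**The concern.** The d = 0.5 cut decides whether Aim 2 supports a larger trial, and its defence (medium effect, NNT about 3.62) concerns how far apart two groups of patients are. The Aim 2 paragraph puts the same cut on the interaction, which measures how much that separation changes between sessions. A large interaction can go with a large benefit, a small one or none, so the defence does not carry over.

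The contrasts named for faster gains may also point the wrong way. Each reverse Helmert contrast compares a session with the average of the sessions before it, so a drug effect that arrives late scores higher than one that arrives early.

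Finally, three parts of the plan give three rules for the same claim. After unblinding, an analyst could follow any of them and reach a different Go decision.

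**Working it through.** **1. The plan's own figure.** Input: d = 0.5 (Outcome and Go Decisions). For two normal patient distributions with a common SD, NNT = 1/(2Φ(d/√2) − 1).

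- Φ(0.5/√2) = Φ(0.3536) = 0.63816
- 2 × 0.63816 − 1 = 0.27633
- 1/0.27633 = 3.62, as stated

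Other conversions tried do not give 3.62: control response rates of 10% to 50% give 5.07 to 8.53, and the binomial effect-size display gives 4.12. The stated NNT therefore belongs to a group difference in between-patient SD units.

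**2. What the contrasts reward.** Input: levels 10, 20 and 30, as listed in the Aim 2 paragraph. Let e10, e20 and e30 be the MEM minus PBO differences in improvement, in outcome SD units. The interaction contrasts are A = e20 − e10 and B = e30 − (e10 + e20)/2. The patterns are invented for illustration.

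| Pattern | e10, e20, e30 | A | B | Mean effect |
|---|---|---|---|---|
| Early and steady | 0.5, 0.5, 0.5 | 0 | 0 | 0.50 |
| Early, placebo catches up | 0.5, 0.5, 0.2 | 0 | −0.30 | 0.40 |
| Late only | 0, 0.1, 0.5 | 0.10 | 0.45 | 0.20 |
| Worse early, equal at 30 | −0.45, −0.45, 0 | 0 | 0.45 | −0.30 |

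The two early patterns score zero or negative. The late pattern scores 0.45. So does the last row, in which the drug is better at no session. If the sign were ignored, the rule could not tell earlier from later benefit.

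**3. Size of an interaction d of 0.5.** Assumptions: equal variances, a common between-session correlation ρ, and d scaled by the between-patient SD of contrast B. The documents give no ρ for the Aim 2 outcomes. The range 0.5 to 0.8 is assumed; 0.8 appears only in the Aim 1 power statement.

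Var(B) = σ²[1 + (1 + ρ)/2 − 2ρ] = 1.5(1 − ρ)σ²

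- ρ = 0.5: SD = √0.75 = 0.866; 0.5 × 0.866 = 0.43 outcome SD; NNT 4.2
- ρ = 0.8: SD = √0.30 = 0.548; 0.5 × 0.548 = 0.27 outcome SD; NNT 6.5

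On this scale the late-only pattern (B = 0.45) has d = 0.45/0.866 = 0.52 at ρ = 0.5 and 0.45/0.548 = 0.82 at ρ = 0.8. It passes the cut across the range, although its mean effect is only 0.20.

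**4. The three rules for faster gains side by side.**

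| Place | Interaction | Then |
|---|---|---|
| Aim 2 paragraph | d > 0.5 | nothing further |
| Table 1 item 3 | p < 0.05 | MEM better at a session or combination, under the d > 0.5 heading |
| Section 4.4 | significant | significant group difference before 30 h |

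Only section 4.4 requires the difference to appear before the end of training.

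**The case against.** The best defence is that Table 1 already holds a sensible rule and the Aim 2 paragraph is a loose summary of it. The first half stands and makes the repair cheap. The second is not secure, because the paragraph names the interaction, lists its sessions and calls the cut primary.

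The contrast argument depends on the levels. Section 4.4 uses data from baseline. If baseline is a level, the first contrast is session 10 against baseline, and a steady early advantage of 0.5 gives 0.5 there. That stands, but the Aim 2 paragraph lists only sessions 10, 20 and 30 and does not say which contrast counts. A steady early advantage could also still earn a Go as a greater gain through the main effect; what is lost is its recognition as faster.

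Three stronger readings are tempting, and the documents do not support them.

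- *The NNT of 3.62 holds only for a baseline-SD scale.* The outcomes are defined as change from baseline, and the SD of change is also a between-patient SD, so 3.62 holds for improvement on that scale. The SD of change is √(2(1 − ρ)) times the baseline SD, so the two coincide at ρ = 0.5.
- *The software scales d by the residual SD, so 0.5 means a much smaller benefit.* No section says so; the package is named without a formula.
- *The chance of a false Go can be read off the cut.* A figure based on the session-30 change covers one outcome and one criterion. It does not address the interaction, and a Go also needs APS learning at p < 0.05 and no significant excess of adverse effects.

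**Conclusion.** The point holds for the interaction. A d above 0.5 on the drug-by-session term is not the effect the plan justifies, and on the listed sessions it favours later growth over earlier gain. It also contradicts Table 1 item 3 and section 4.4. The direction result is plain arithmetic and needs only that sessions 10, 20 and 30 are the levels. The size, 0.43 to 0.27 outcome SD (NNT 4.2 to 6.5), is illustrative and rests on the assumed correlation and on scaling by the contrast's own SD.

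For the main effect, the unnamed SD is a gap to close, not a demonstrated error. The stated NNT is correct for a group difference on a between-patient scale.

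**What to change.** - In the Aim 2 paragraph, remove the d > 0.5 cut from the interaction.
- For faster gains, use the Table 1 gate (interaction p < 0.05), followed by d > 0.5 for the MEM minus PBO difference in change from baseline at a session before session 30. Align Table 1 and section 4.4 with this wording.
- State the session levels in the interaction test. Without baseline as a level, the gate too would miss a steady early advantage.
- Name one between-patient SD (baseline SD or SD of change) for all Aim 2 Go criteria, fix it before unblinding, and report each d with a 95% CI. Either choice is defensible.
- Limit the NNT statement to d values for group differences.

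The cost is a few sentences in the plan and minor code. The downside is that the faster criterion becomes somewhat stricter than under the Aim 2 paragraph alone, in a study whose own text (Research Strategy, item 10) expects difficulty reaching p < 0.05 for group differences.
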